GCP – Good Clinical Practice

HGV – Heavy Goods Vehicles

ICL – Imperial College London

IONA – Assessing the impact of non-tailpipe emission from traffic on the asthmatic airway

IgE - Immunoglobulin E

ISC – Independent Scientific Committee

Kph – Kilometres Per Hour

LAQN – London Air Quality Network

LGV Light Goods Vehicles

Mph – Miles Per Hour

NTE – Non-tailpipe emissions

NO₂ – Nitrogen Dioxide

O₃ - ozone

PI – Principal Investigator

PM – Particulate Matter

PMG – Project Management Group

PPI – Public and patient Involvement

QMUL – Queen Mary, University of London

SOP – Standard Operating Procedures.

TLC – Tidal Lung Capacity

UK – United Kingdom

3. Signature page

CI Agreement

The study, as detailed within this Research Protocol, will be conducted in accordance with the principles of Good Clinical Practice (GCP), the UK Policy Framework for Health and Social Care Research, and the Declaration of Helsinki and any other applicable regulations. I agree to take responsibility for the statistical analysis and oversight of this study.

CI Name: [name]

Signature:

Date: 23/06/2022

4. Summary and synopsis

Short title	(IONA) Assessing the impact of non-tailpipe emissions from traffic on the asthmatic airway
Methodology	Randomised experimental three condition crossover panel study
Objectives / aims	
Objective 1: Assess and compare the acute health effects: changes in lung function and airway inflammation, in mild/moderate asthmatics exposed at three selected microenvironments with contrasting traffic profiles to increase contrast in particulates from brake wear, tyre wear, and road abrasion.
 
Objective 2: Provision of an air pollutant database (PM_{2.5} and PM₁₀ mass and chemical composition, PNC and NO₂) and a time series of source apportioned PM_{2.5} and PM₁₀ covering all exposure days at the three

	
selected sites.
 
Objective 3: Examine the relationship between variations in daily non-tailpipe source fractions derived from tire, brake and road wear, with the deposited dose determined in the nasal airways and the physiologic and immunologic responses observed.
 
Objective 4: Provision of a biobank of plasma samples for future work examining molecular signature of exposure and response.

Number of participants	48
Inclusion and exclusion criteria	
Inclusion criteria:
 
 • Doctor diagnosed asthma starting on or before age 16 years • Prescribed regular inhaled corticosteroid medication • Able to use a static exercise bicycle for the study duration 
Exclusion criteria:
 
 • Tobacco smoking, or living with smoker • Body mass index (BMI) > 30 • Asthma hospitalisation within 12 months • Three or more asthma episodes requiring oral corticosteroid medication within 12 months • Other major lung disease • Chest surgery within 6 months • Unable to give informed consent • Occupational exposure to particulate matter (PM) or high levels of air pollution
Statistical methodology and analysis (if applicable)	Mixed effects models, taking into account repeated measurements within participants.
Study duration	01/08/2022- 1/12/2024

5. Introduction

5.1. Background

The global burden of disease survey estimated air pollution contributed to one in eight deaths in 2019¹. Urban areas such as London are a heterogeneous patchwork of different air pollutants, which all have different impacts on human health. Air pollution disproportionately impacts people living with asthma, increasing hospital admissions² and the likelihood of death³. Reports suggest that 65% of asthma deaths could be avoided by suitable primary care support⁴. Understanding how different air quality environments affects people living with asthma will improve asthma management in primary care by increasing the specificity guidance provided to people with asthma.

In an effort to reduce air pollution a number of government and industrial policies have been developed to increase sales of electric and hybrid cars. Electric and hybrid vehicles produce less air pollution from exhausts but due to their increased weight, they increase air pollution from tyre and road wear with an uncertain contribution from brake wear. Particles arising from tyre and brake wear, as well as the resuspension of road dust represent a greater proportion of roadside PM by mass than direct tailpipe emissions. As tailpipe emissions will decrease as nations strive to meet their NetZero commitments, greater attention on non-tailpipe sources is urgently required to evaluate their relative hazard compared with other pollutant sources. Our previous *in vitro* studies on dendritic cells and airway macrophages have indicated enhanced immune responses with the coarse particulate fraction (PM_{2.5-10}) from non-tailpipe constituents⁵. To date no research has explored the health impacts of non-tailpipe air pollution on human health in a real-world setting.

5.2. Rationale

In an effort to reduce air pollution a number of government and industrial policies have been developed to increase sales of electric and hybrid cars. Electric and hybrid vehicles produce less air pollution from exhausts but due to their increased weight, they increase air pollution from tyre and road wear with an uncertain contribution from brake wear. Air pollution particles arising from tyre and brake wear, as well as resuspension of road dust, now represent a greater proportion of roadside PM by mass than direct tailpipe emissions. These Non-Tailpipe Emissions (NTE) remain unregulated, and their health impacts under explored, particularly in vulnerable groups.

Previous work by our team⁶⁻¹² demonstrated the feasibility of a quasi-experimental human real-world exposures using a crossover design for disentangling relative contributions of pollutant metrics on acute cardiopulmonary endpoints in healthy adults. Whilst this work showed the key role played by primary gaseous and particulate emissions, the study focused on responses in healthy adults and did not

examine biological pathways likely to lead to symptom exacerbation in vulnerable asthmatic populations. The study did examine a range of metals such as Fe, Cu, Ni and V, reflecting their capacity to cause oxidative stress, but did not explicitly relate these to NTEs, nor employ them for detailed source apportionment.

Our previous work has consistently shown that coarse mode PM is more effective at driving dendritic cell maturation and T-cell activation, than PM_{2.5} samples from urban background and roadside sites, or freshly collected diesel tailpipe PM. Given that such changes were observed in vitro this provides suitable rationale that health changes may be observed in asthmatic participants as people living with asthma are uniquely sensitive to the impacts of air pollution.

To date, no research has explored whether real-world NTE are causally related to worsening of asthma. Therefore, we aim to explore the hypothesis that clinically important adverse acute asthmatic responses are driven by non-tailpipe components within coarse mode PM.

6. Study objectives

6.1. Primary objective

Objective 1: Assess and compare the acute health effects: changes in lung function and airway inflammation, in mild/moderate asthmatics exposed at three selected microenvironments with contrasting traffic profiles to increase contrast in particulates from brake wear, tyre wear, and road abrasion.

6.2. Secondary objective

Objective 2: Provision of an air pollutant database (PM_{2.5} and PM₁₀ mass and chemical composition, PNC and NO₂) and a time series of source apportioned PM_{2.5} and PM₁₀ covering all exposure days at the three selected sites.

Objective 3: Examine the relationship between variations in daily non-tailpipe source fractions derived from tire, brake and road wear, with the deposited dose determined in the nasal airways and the physiologic and immunologic responses observed.

Objective 4: Provision of a biobank of plasma and nasal mucus samples for future work examining molecular signature of exposure and response.

6.3. Primary endpoint

- Lung function as measured by Forced Expiratory Volume in one second (FEV1)

Secondary endpoint

- Spirometry (FVC, FVC/FEV1 ratio, z Scores)
- Fractional Expired Nitric Oxide (FeNO)
- Peak expiratory flow
- Oscillometry
- Asthma symptoms
- Asthma control Test
- Quality of Life: AQLQ
- Immune responses: damage-associated molecular patterns (DAMPs) and alarmins, such as high mobility group box 1 (HMGB1) S100 proteins, myeloperoxidase-DNA complexes (MPO-DNA), IL-33, Th2 and Th17 cytokines and metal deposition in the nasal airways

Control variables

- Estimated VO2max
- Heart rate
- Air quality measured as: PM10 and PM2.5, particle number concentration (PNC) and gaseous pollutants ozone (O3), nitrogen dioxide (NO2), black carbon.
- Pollen count
- Temperature and humidity
- Physical activity (accelerometry)
- Personal air quality (Plume labs)

Biobanking

- Venous blood
- Nasal Mucus
- Urine

Banking

- PM filters

7. Study population

Asthma is a complex disease now recognized to include multiple phenotypes. Therefore, to ensure maximum generalisability of our findings, we will recruit participants with the most common phenotype: allergic asthma that started in childhood/adolescence. We will exclude those with a BMI >30 to exclude obese, steroid-resistant phenotypes. Participants (male and female) recruited to the study will be over 18 years old with mild to moderate stable asthma. We will exclude those

hospitalized with an asthma attack in the last 12 months, and those with more than three episodes requiring oral corticosteroids in the last 12 months. To reduce the impact of confounders participants must neither smoke, nor live with current smokers, must live within greater London, and have no occupational exposure to PM or oxidant gases.

With input and guidance from our active patient and public involvement group at the Asthma UK Centre for Applied Research (AUKCAR), participants will be recruited from primary care.

7.1. Recruitment

Primary Care settings

Guided by experts within the Primary Care CRN teams and by NOCLOR, we will use a PIC site approach. In the first instance participants will be recruited via general practice. We will approach general practices in East London with the help of [name], research lead for North East London Integrated Care Board, inviting them to act as PIC sites and other areas of central London with the help of NOCLOR.

With guidance from the study team, a member of the practice administrative team, GP or practice nurse will run searches of their patient electronic health records using READ / SNOMED codes to identify eligible patients according to the study inclusion / exclusion criteria.

Eligible participants identified by searches will be approached via secure electronic mail out using AccuRx, with an invitation to join the study. The invitation will provide a very brief summary of the study with a link to the Patient Information Sheet and further information on the IONA study website, through which they can express an interest in participation, and provide contact details. A draft text can be found at *SMS text example V0.2 28.02.23*

Once potential participants have expressed an interest in the study, [name] will contact them by phone or a Teams/Zoom call to discuss the study, clarifying any points and answering questions. Potential participants will have at least 24 hours to consider participation. To confirm their consent, they will have the option of emailing copies of signed consent forms to [name], or signing consent forms at the first study visit.

As an NIHR portfolio study, we will seek Service Support Costs and CRN support for recruitment.

Non primary care settings

If recruitment in primary care proves ineffective, our secondary recruitment approach will target people with asthma who study and work in Queen Mary, University of London and Imperial College London. With input and guidance from our active patient and public involvement group at the Asthma UK Centre for Applied Research (AUKCAR), participants will be recruited from research lists, lecture visits, posters and social media mail outs across the university campuses and general population. Participants may be university students and staff. However if participants are members of staff or students they will not be recruited by members of staff in direct supervisory roles.

Example recruitment documents:

Lecture slide (LINK)

Poster (LINK)

SMS template (LINK)

Email template (LINK)

Website Copytext. (LINK)

7.2. Inclusion criteria

Inclusion criteria:

- Doctor diagnosed asthma starting on or before age 16 years
- Prescribed regular inhaled corticosteroid medication
- Able to use a static exercise bicycle for the study duration

7.3. Exclusion criteria

- Tobacco smoking, or living with smoker
- BMI > 30
- Asthma hospitalisation within 12 months
- Three or more asthma episodes requiring oral corticosteroid medication within 12 months
- Other major lung disease
- Chest surgery within 6 months
- Unable to give informed consent
- Occupational exposure to PM or high levels of air pollution
- Under the age of 18
- Women at any stage of pregnancy
- Any breast feeding women

Occupational exposure is defined as people who work as Taxi drivers, couriers, waste removal drivers and utility services drivers. If other occupations with high exposure to pollution need to be considered the study team will discuss potential eligibility with the PMG group, comprising of experts in air pollution and asthma management.

8. Study design

Randomized cross-over semi-experimental panel study

9. Study procedures

9.1. Pilot Study

A pilot study will be completed to future explore the efficacy of the study design. The pilot will be completed following the same protocol outlined in this document in sections 9.2 to 19.1 with the following alterations:

Recruitment:

20 participants will be recruited in a convenience sample using the following inclusion and exclusion criteria:

Inclusion:

- Healthy participants with no known respiratory health issues.
- Able to exercise intermittently for two hours
- No surgery within 12months

Exclusion:

- Unable to give informed consent
- Occupational exposure to PM or high levels of air pollution
- Under the age of 18
- Women at any stage of pregnancy
- Any breast feeding women

Screening:

As the exclusion criteria prohibits participants with respiratory health issues pilot participants will not provide a screening blood sample (4 x 10ml in single draw) for eosinophil levels, and specific common aero-allergens immunoglobulin E (IgE) levels.

Expenses:

Only expenses pertaining to travel will be paid to participants of the pilot study.

Biobank:

Due to the novelty of the research we will biobank samples from the pilot study in accordance to the procedures outlined in section 14.

Dissemination:

- Findings will be disseminated to the study team and PPI group to inform any decision making prior to the commencement of data collection for IONA.
- There is no intention at this time to compare health to asthmatic data, due to likely differences in air quality. However findings will still be highly novel and we will still seek to publish in peer reviewed journals.

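### The pilot's own eligibility list (9.1) omits the main trial's exclusion of smokers and people living with smokers and gives no reason, although the stated reason for that exclusion applies equally to healthy volunteers.

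*Protocol*

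**What the plan says.** Section 7.3 excludes from the main trial "Tobacco smoking, or living with smoker", and the synopsis in section 4 repeats this. Section 7 (Study population) gives the reason: "To reduce the impact of confounders participants must neither smoke, nor live with current smokers".

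The pilot in section 9.1 is set up separately. On procedures it says "The pilot will be completed following the same protocol outlined in this document in sections 9.2 to 19.1 with the following alterations". On entry it says "20 participants will be recruited in a convenience sample using the following inclusion and exclusion criteria". Its inclusion criteria begin with "Healthy participants with no known respiratory health issues" and add ability to exercise and no recent surgery. Its exclusions are inability to consent, "Occupational exposure to PM or high levels of air pollution", age under 18, pregnancy and breast feeding. Smoking is not mentioned, either by the participant or in the household.

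Section 9.1 also states how the pilot will be used. Its findings go to the study team and the PPI group for decisions taken before the main data collection starts, its samples are biobanked, and on publication it says "However findings will still be highly novel and we will still seek to publish in peer reviewed journals".

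**The concern.** The main trial treats tobacco smoke as a competing exposure to be kept out. The pilot uses the same sites, the same exercise and exposure session and the same airway and nasal measurements, yet its entry list does not keep tobacco smoke out.

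The design takes trouble over other exposures. Participants travel by taxi with the windows closed so that exposure before testing is controlled (9.3), and people with occupational particulate exposure are excluded. A volunteer who smokes on the morning of a visit, or between the session and the next-day visit, adds a particle exposure that these measures do not cover. At stake is how cleanly a study of 20 people can measure FeNO, nasal metal deposition and injury or immune markers. Entry criteria cannot be corrected once the samples have been taken.

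**Working it through.** No figure in the plan is in dispute, and the pilot's 20 is given without a derivation, so there is nothing to reproduce. The check is a comparison of text, followed by a short illustration.

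**1. Does section 7.3 still apply to the pilot?** The pilot inherits a range that starts at 9.2, and section 7 lies before it. (The stated end of the range, 19.1, does not exist as a section, but the point depends only on the start.) The 9.1 list also repeats several 7.3 items, which would be redundant if 7.3 still applied. The list therefore replaces 7.3. Nothing from 9.2 onward restricts smoking.

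**2. What happened to each of the eleven items in 7.3?**

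| 7.3 item | In the 9.1 list |
|---|---|
| Consent, occupational exposure, age, pregnancy, breast feeding (5 items) | Kept |
| Other lung disease; chest surgery (2) | Replaced by a respiratory-health criterion and a wider surgery criterion |
| Asthma admission; oral steroid episodes; BMI (3) | Dropped; the first two are specific to asthma, and section 7 ties BMI to an asthma phenotype |
| Smoking or living with a smoker (1) | Dropped, no reason given |

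5 + 2 + 3 + 1 = 11. Smoking is the only dropped item whose stated justification does not depend on asthma. Being healthy without known respiratory problems does not rule out a smoker who has no diagnosed disease.

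**3. What does the crossover remove?** Write the pre-to-post change for person *i* at site *s* as

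Y(i,s) = site(s) + person(i) + b·X(i) + c(s)·X(i) + d·S(i,s) + error(i,s),

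where X is stable smoking status and S is smoke exposure around that particular visit. The difference between sites *s* and *t* within a person is

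site(s) − site(t) + [c(s) − c(t)]·X(i) + d·[S(i,s) − S(i,t)] + error(i,s) − error(i,t).

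- The b·X(i) term cancels, so stable status does not bias the site contrast.
- The c terms remain if smokers respond differently to the sites (effect modification).
- The d term remains and acts as extra variability, unless smoking differs systematically by site. The documents give no reason to expect that.

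**4. How likely is it that a smoker enters?** The documents give no prevalence, so p is an assumption. With n = 20, the expected number is 20p and P(at least one) = 1 − (1 − p)^20.

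| Assumed p | Expected smokers | P(at least one) |
|---|---|---|
| 5% | 1 | 1 − 0.95^20 = 0.64 |
| 10% | 2 | 1 − 0.90^20 = 0.88 |
| 15% | 3 | 1 − 0.85^20 = 0.96 |
| 20% | 4 | 1 − 0.80^20 = 0.99 |

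Non-smokers who live with a smoker would be additional. These figures show how likely a smoker is to be enrolled. They do not measure bias, variance inflation or loss of power.

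**The case against.** The strongest reply is that a healthy-volunteer pilot may reasonably use wider entry criteria, and that little follows from it here. Several parts of that reply stand.

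- A reader might infer that smokers would confound the pilot's site comparisons. The documents do not support that. Participants are their own controls, each session has its own pre-exposure baseline, and stable status cancels as shown.
- A reader might infer that a few smokers would dominate the variance and mislead the design of the main trial. The documents do not support that either. They give no variance for smokers, and section 9.1 says only that findings inform decisions, without naming a variance, effect size or threshold to be carried forward. The main-trial difference and standard deviation in 10.1 come from a cited study of diesel traffic exposure in people with asthma. Section 9.1 also disclaims any present intention to compare the pilot with the asthma data.
- Overnight smoking can reach only the next-day measures, because on exposure days participants are at the site from 10:00 until about 14:00.
- Smoke exposure may be partly captured. Personal air-quality monitors are worn for three days before each exposure visit, a baseline questionnaire of unseen content is given at screening, and the individual covariates in 10.3 are introduced as examples, so that list is open.

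What does not stand is the suggestion that the omission is simply a wider criterion chosen on purpose. No reason is given, and the parallel occupational exclusion is kept. The personal monitoring is scheduled before the exposure visit, so it does not cover the interval to the next-day tests. Smoking is not among the covariates named.

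**Conclusion.** The point holds as a minor one. Followed as written, 9.1 admits smokers and people living with smokers, against a principle that section 7 states without reference to asthma, and nothing later in the protocol restores the exclusion.

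The consequence is limited to the pilot: visit-to-visit smoke exposure, possible effect modification, and avoidable noise in FeNO, nasal metal and mediator measures. The size of that noise cannot be derived from the documents. Enrolling at least one smoker is more likely than not across the whole assumed range of prevalence, but that range is an assumption. The conclusion itself rests on the comparison of the two lists and does not depend on it.

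**What to change.** Add to the exclusions in 9.1 the same item as in 7.3: "Tobacco smoking, or living with smoker". This is one line, and the cost is a slightly smaller pool of volunteers for a sample of 20.

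If the omission is intended, say so in 9.1 with the reason, record smoking status and recent smoke exposure (own and household) at each visit, including the next-day visit, and state how the pilot analysis will account for them. This keeps the wider pool, at the cost of a few extra questions per visit and an additional factor to handle in a small data set.

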9.2. Overview

48 participants with mild and moderate asthma will be recruited from QMUL and Imperial College London universities and research lists into a single experimental group. Participants will visit the field-testing sites located in three different air quality environments in a randomised cross over design. Sites targeted will be:

- (1) A busy road junction characterized by **stop-go traffic** to enhance emissions from brake wear
- (2) **High speed continuous traffic**, to enhance tire wear emissions
- (3) An **urban background** site away from clear traffic sources

During the exposure protocol participants will ride on a static bike for two hours at a standardised intermittent intensity. Participants will perform identical respiratory health assessment following the exercise task. In parallel to exposures at sites we will perform real-time measurements of PM10 and PM2.5, particle number concentration (PNC) and gaseous pollutants ozone (O3), nitrogen dioxide (NO2), black carbon.

